The current study will provide critical preliminary data for a larger clinical trial that will test the effects of iTBS to the dlPFC and iTBS to the dmPFC compared to sham on both cocaine use and physiological measures of reward functioning. The pilot study will focus on assessing the effects of dmPFC alone, as prior studies have already indicated that iTBS to the dlPFC can alter EEG^{91,92}. We hypothesize that reward sensitivity and cue reactivity, as measured by RewP and LPP, respectively, will demonstrate utility as biomarkers of TMS effects. There is an urgent need to improve treatments for CUD in the wake of recent trends indicating rising cocaine use and overdose deaths⁹³. Research indicates that a decreased RewP to wins and increased LPP to cocaine cues are potential targetable physiological patterns for TMS manipulation. This proposal is significant because it will 1) establish feasibility of a novel stimulation site utilizing a biomarker approach and 2) lay the ground work for a future larger clinical trial comparing the novel site to a traditional site and sham. For the main study, we will compare the effects of dmPFC to dlPFC and sham. We hypothesize that dmPFC compared to dlPFC or sham will lead to greater changes in EEG measures of reward functioning (i.e., RewP and LPP).

Aims and Hypotheses

Pilot Study

Specific Aim 1: To assess the effects of active iTBS to dmPFC on EEG measures of reward sensitivity and cue reactivity.
Hypothesis 1a: Primary hypothesis: iTBS will increase the amplitude of the RewP and switch the drug>pleasant LPP bias to pleasant>drug compared to sham iTBS.

Specific Aim 2: To assess the effects of active iTBS to dmPFC on cocaine craving in cocaine users.

Hypothesis 2a: Primary hypothesis: iTBS to dmPFC compared to sham iTBS will reduce cocaine craving (Minnesota Cocaine Craving Scale) in cocaine users.

Primary Outcome Measures

1. Reward sensitivity as assessed by the Reward Positivity – the RewP is an EEG component that will be measured immediately before and immediately following iTBS sessions on the test day.
2. Cue reactivity as assessed by the Late Positive Potential to drug vs. pleasant cues – the LPP is an EEG component that will be measured immediately before and immediately following iTBS sessions on the test days.

Secondary Outcome Measures

1. Craving – craving will be assessed immediately before and immediately following iTBS sessions on the test days.

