2. Pain – pain will be assessed via a Visual Analogue Scale (1-10) immediately before and immediately following iTBS sessions on the test days.
3. Cognitive function – a brief assessment of cognitive function will be included immediately before and after the iTBS sessions on the test days.

Main Trial

AIM 1: Assess effects of iTBS to left dlPFC and dmPFC compared to sham on reward sensitivity.

Primary Hypothesis 1a: Active iTBS relative to sham will increase the amplitude of the RewP/delta power to rewards compared to non-rewards.

Exploratory Hypothesis 1b: iTBS to dmPFC will result in a greater increase in the RewP/delta power compared to dlPFC.

AIM 2: Assess effects of iTBS to left dlPFC and dmPFC compared to sham on motivated attention.

Primary Hypothesis 2a: Active iTBS relative to sham will switch the drug>pleasant LPP bias.

Exploratory Hypothesis 2b: iTBS to dmPFC will result in a greater increase in LPP to pleasant images.

EXPLORATORY AIM 3: Identify individual differences in iTBS response with baseline characteristics.

Exploratory Hypothesis 3a: We will explore CUD severity, impulsivity, and craving as predictors of iTBS effects.

Primary Outcome Measures

1. Reward sensitivity as assessed by the Reward Positivity – the RewP is an EEG component that will be measured immediately before and immediately following iTBS sessions on the test day.
2. Cue reactivity as assessed by the Late Positive Potential to drug vs. pleasant cues – the LPP is an EEG component that will be measured immediately before and immediately following iTBS sessions on the test days.

Secondary Outcome Measures

1. Craving – craving via the Minnesota Cocaine Craving scale will be assessed immediately before and immediately following iTBS sessions on the test days.
2. Pain – pain will be assessed via a Visual Analogue Scale (1-10) immediately before and immediately following iTBS sessions on the test days.
3. Cognitive function – a brief assessment of cognitive function will be included immediately before and after the iTBS sessions on the test days.
4. Behavioral reward learning – participants will complete the Pavlovian Go/No-Go task before and after iTBS sessions.
5. Anhedonia – the Snaith Hamilton Pleasure Scale (SHAPS) will be collected before and after iTBS sessions.

Study design

Pilot Study

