delivered with a MagVenture Mag Pro R30 with the Cool-B70 A/P coil with active liquid cooling and active/sham sides (Farum, Denmark). A member of the CNRA not involved in the study will be the only person aware of the randomization results and will program the system to ensure double blinding.). For dmPFC, we will measure approximately 25% of the nasion-inion distance, or Talairah coordinates X 0 Y+60 Z+60^{32,98}. The first session will begin with the acquisition of the resting motor threshold (rMT; lowest stimulus intensity that elicits a visible twitch on 50% of the trials) on the contralateral hand. iTBS (triplet 50 Hz bursts, repeated at 5 Hz, 2 sec on and 8 sec off; 600 pulses per session) will be delivered at 80% of the rMT and will last ~3 minutes, consistent with current EEG-iTBS single day protocols^{73,99}. The intensity can be lowered if the participant cannot tolerate the stimulation. Each participant will receive 2 sessions with a 15-20 minute interval between sessions¹⁰⁰. Participants will complete the EEG protocol before the first iTBS session (baseline) and immediately following the two stimulation sessions. This will conclude participation for the pilot participants.

EEG Protocol. During the tasks described below, EEG electrode cap, amplified with BrainAmp MR and digitized using Brain Vision Recorder (Brain Products, Munich). Before collection, impedances will be maintained below 50 k(OHM). The sampling rate will be 500 Hz and data will be filtered with .1 Hz high-pass and 100 Hz low-pass filters. Resting data will be collected for 3 minutes (90-seconds eyes open and 90-seconds eyes closed). After collection, data reduction will be performed with a combination of programs including Brain Vision Analyzer 2, MATLAB (EEGLab; PCA Toolkit) and BESA. Both traditional windowed ERP (mean amplitude) and TFA approaches will be used to analyze the RewP. The LPP will be defined as the mean amplitude between 400-800ms post stimulus.

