Reward Sensitivity: The Doors Task⁵⁹ will be used to elicit the RewP component, representing reward sensitivity^{47,60}. The task is a guessing game, where participants guess which door contains a reward behind it. After selecting a door, the participants are notified if they found the prize by a green arrow pointing up or if they did not find the prize by a red arrow pointing down. Unknown to the participants, winning and losing outcomes are presented 50% of the time in a random order. The RewP is larger in response to rewards (wins) than non-rewards (losses). Self-reported anhedonia (Snaith Hamilton Pleasure Scale; SHAPS) will also be assessed as a secondary measure of reward sensitivity in addition to the RewP.

Cue Reactivity: The Picture Viewing Task will be used to elicit the LPP, reflecting the motivational salience of a stimulus. During this task, participants are asked to view a slideshow of images including pleasant, unpleasant, neutral, and cocaine-related images⁶¹. Pleasant and unpleasant images elicit a more positive LPP amplitude than neutral images⁵⁵. In cocaine users, the LPP is also larger to cocaine images compared to neutral images, similar to pleasant and unpleasant images^{10,101}.

Other Measures.

Cocaine Use. Urine samples will be collected at the study visit and tested for the cocaine metabolite, benzoylecgonine (BE). Samples containing ≥ 300 ng/ml of BE will be considered positive. Additionally, the Timeline Follow Back¹⁰² method will be used as a secondary self-reported measure of daily cocaine use in the month prior to participating in the study. These measures will be used to assess severity of cocaine use.

Cocaine Craving. Cocaine craving will be measured using the Minnesota Cocaine Craving Scale (MCCS)¹⁰³. The MCCS is a widely used and reliable self-report measure of craving for cocaine, with 3 subscales (craving intensity, frequency, duration) and will be assessed before and after the EEG session.

Cognitive Function. The Montreal Cognitive Assessment (MoCA)¹⁰⁴ assesses multiple cognitive domains including attention, concentration, executive functions, memory, language, visuospatial skills, abstraction, calculation, and orientation. The MoCA will be administered twice on each study session day, prior to the first iTBS session and after the second iTBS session. Alternative equivalent forms will be used for the pre- and post-tests.

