Safety outcomes. We will collect the following before the iTBS sessions: hours of sleep, UDS/TLFB, breathalyzer, the AE/SAE form, pain, and the Cocaine Selective Severity Assessment (CSSA – a measure of withdrawal). The AE/SAE form and pain will also be completed after the iTBS session. See Table 2 for the Study Visit Timeline.

[figure not shown]

Table 2. Study Visit Timeline – Pilot Study

[figure not shown]
Assessment	Length of Time	Details
Assess safety:	5-10 min	UDS, TLFB, pregnancy, sleep, CSSA, C-SSRS, AE/SAE form
Cognitive Assessment	10 min	MoCA
Fit EEG cap:	30 min	Measure & place cap on head, gel electrodes
Complete EEG Session 1:	35 min	Resting EEG, Doors Task, Picture Viewing Task
Assess rMT:	10 min	Collect resting motor threshold
iTBS Session 1:	3 min	iTBS to dmPFC or sham iTBS
Rest:	15-20 min	Sit quietly
iTBS Session 2	3 min	iTBS to dmPFC or sham iTBS
Assess safety:	5-10 min	AE/SAE form
Cognitive Assessment	10 min	MoCA
Complete EEG Session 2:	35 min	Resting EEG, Doors Task, Picture Viewing Task

Main Trial

Design. The proposed study will use a within-subjects cross over design as shown in *Fig 2*. Non-treatment-seeking adults with a primary CUD diagnosis (N = 75) will complete screening and baseline assessments prior to completing three separate iTBS days (sham, dlPFC iTBS, or dmPFC iTBS), order counterbalanced across participants. On each day, EEG will be collected before and after 3 iTBS successive sessions (15-minutes between sessions). Days will be spaced at least 24-hours apart and will be completed within 2 weeks. We will aim to consent 115 participants to achieve 75 completed.

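### Does the pilot's wording on when EEG and craving are measured conflict with its visit timeline in a way that calls for a change?

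*Combined protocol and SAP*

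**What the plan says.** Five sections of the combined protocol bear on timing in the pilot.

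- **Outcome lists (Aims and Hypotheses, Pilot Study).** For the first primary outcome: "the RewP is an EEG component that will be measured immediately before and immediately following iTBS sessions on the test day". For the second: "the LPP is an EEG component that will be measured immediately before and immediately following iTBS sessions on the test days". For craving: "craving will be assessed immediately before and immediately following iTBS sessions on the test days". For cognition: "a brief assessment of cognitive function will be included immediately before and after the iTBS sessions on the test days".
- **TMS Session.** "Participants will complete the EEG protocol before the first iTBS session (baseline) and immediately following the two stimulation sessions". The same section says that the first stimulation session opens with finding the resting motor threshold.
- **Table 2, Study Visit Timeline.** The order is safety checks, MoCA (10 min), cap fitting (30 min), EEG Session 1 (35 min), motor threshold (10 min), iTBS Session 1 (3 min), rest (15-20 min), iTBS Session 2 (3 min), safety form (5-10 min), MoCA (10 min), and then "Complete EEG Session 2" (35 min). The Safety outcomes paragraph above the table adds: "The AE/SAE form and pain will also be completed after the iTBS session".
- **Cocaine Craving (Other Measures).** The craving scale "will be assessed before and after the EEG session".
- **Specific Analyses.** RewP, LPP, craving, pain and MoCA are each modelled on time (before or after stimulation) and location (dmPFC or sham). LPP also has image type.

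**The concern.** Two things look wrong. First, the primary outcomes are described as taken straight after stimulation, yet the timeline places two other assessments in between. If a stimulation effect fades quickly, the EEG would catch less of it than the definition implies. The cognition wording looks worse still, because the first MoCA comes before cap fitting and the whole first EEG.

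Second, craving has two descriptions. Each test day has two EEG sessions, so timing the rating around 'the' EEG session is ambiguous. Staff following that paragraph could take the second rating after a set of cocaine images, and staff following the outcome list could take it before. If both ratings were placed around a single EEG session, they would not span stimulation and the Aim 2 model could not be fitted as written. A pilot that sets out to test its assessment procedures should be clear about this.

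**Working it through.** **Inputs.** All durations are from Table 2: safety form 5-10 min, MoCA 10, cap fitting 30, EEG 35, motor threshold 10, each iTBS session 3, rest 15-20. Resting EEG is 3 min (EEG Protocol). The plan states no interval of its own, so there is no figure to reproduce. The sums allow no time for moving between steps.

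**EEG after stimulation**
- Start: (5 to 10) + 10 = 15 to 20 min after iTBS Session 2.
- First ERP task, if resting EEG comes first as listed: (15 to 20) + 3 = 18 to 23 min.
- End: (15 to 20) + 35 = 50 to 55 min.

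The mismatch with the definition is therefore about 15-20 min. The post-stimulation pain rating need not lengthen it. Pain is listed under Safety outcomes, and Table 2 has a safety row at that point. The Details column of that table is not exhaustive: the safety row before stimulation omits pain and the breathalyzer, although the paragraph requires both.

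**EEG before stimulation.** Table 2 puts 10 min of motor threshold between EEG Session 1 and iTBS Session 1. The TMS Session section makes that step the opening of the stimulation session, so on that text the EEG does end directly before the session begins. This is not a conflict.

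**MoCA.** The first MoCA ends 30 + 35 + 10 = 75 min before iTBS Session 1. The second starts 5 to 10 min after iTBS Session 2. The Cognitive Function paragraph and the notes to Table 1 ask only that it precede the first stimulation and follow the second, and Table 2 does that. Only the adverb in the outcome list is off.

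**Craving, three readings**

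| Reading | Time between ratings | Spans stimulation? |
|---|---|---|
| Directly around stimulation (outcome list) | 3 + (15 to 20) + 3 = 21 to 26 min | Yes |
| Before EEG 1, after EEG 2 | 35 + 10 + 3 + (15 to 20) + 3 + (5 to 10) + 10 + 35 = 116 to 126 min | Yes |
| Around one EEG session | 35 min | No |

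The second reading includes 35 + 35 = 70 min of EEG with both sets of cocaine images. It still meets the Aim 2 model, which asks only for ratings before and after stimulation. The third contradicts the outcome list and the model, and would leave Hypothesis 2a untestable, so a reader with the whole document would set it aside.

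**Effect on the comparison.** The contrast of interest is (post minus pre, dmPFC day) minus (post minus pre, sham day), within participant. If the same timing is used on both days, a shift that comes only from elapsed time or from viewing images, and is equal on the two days, cancels. A fading stimulation effect would not cancel. The documents give no rate of decay, so its size cannot be worked out.

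**The case for a change.** The best case for a change is that a primary outcome definition should agree with the schedule that produces the data, especially in a pilot meant to show that the assessments can be run as written. With five participants, one craving rating taken at a different point is a visible share of the data. The corrections would be a few words and one fixed slot for a scale already in use.

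Part of this stands. The 15-20 min and 75 min gaps are facts of Table 2, and the two craving descriptions do differ. The readable schedule does not settle craving: Table 1 marks only the visit, and Table 2 has no readable craving row. Figures beside Table 2 are missing from the text at hand, so a missing row cannot be counted against the plan.

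The need for a change does not stand. Rewording the EEG and MoCA timing would leave every step where it is. Moving steps has costs of its own. Recording EEG before the MoCA would start it at 5-10 min, but would push the MoCA to (5 to 10) + 35 = 40 to 45 min after stimulation, behind an EEG session that the risk section says may leave participants tired or bored. It would also lose the matching order of MoCA then EEG on both sides of stimulation. Fixing craving directly around stimulation would put the first rating after one set of cocaine images and the second before the other set. Spanning both EEG sessions includes both sets. Either is defensible.

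**Conclusion.** The mismatches are real but slight, and no change to the plan follows. 'Immediately following' stands for about 15-20 min, a time the plan sets out openly in Table 2. The outcome remains a same-visit measurement before and after stimulation, and no sample size, model or decision rule depends on the adverb. The cognition wording is a clerical slip. The craving ambiguity is a gap that the outcome list, Hypothesis 2a and the Aim 2 model together let staff and analysts fill sensibly, with one rating on each side of stimulation.

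This rests on three assumptions: Table 2 is the order followed at visits, staff use one craving timing on both test days, and the single-session reading of the craving paragraph is not adopted. The pilot's sample size section says that the aim is feasibility and that estimates from five people are not expected to generalise. Any loss of effect over the 15-20 min cannot be sized from the documents, and they give no sign that it differs between active and sham days in a way that rewording would cure.

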Cue reactivity as a target in treating CUD with TMS.

The LPP is an ERP component occurring over the centro-parietal electrodes (starting ~400ms post stimulus) that is larger to unpleasant and pleasant compared to neutral images^{78,79}. The LPP is thought to be marker of motivated attention toward emotionally salient cues and cue reactivity⁸⁰, as studies in drug users show that the LPP is enhanced in response to drug cues^{10,81-84} and is associated with craving⁸⁴. The LPP is thought to arise from a complex network of brain areas, including the visual cortex, amygdala, prefrontal cortex, and insula⁸⁵⁻⁸⁷. Further, visual representations of rewarding stimuli are mediated by the dopamine system⁸⁸ and thus, LPP could be altered by TMS manipulation via these networks. Importantly, the LPP changes with treatment and abstinence status⁸⁹ and is altered by TMS over the PFC. In one study, prior to treatment cocaine users displayed a larger LPP response to drug compared to pleasant images, and this pattern flipped after treatment¹⁰. Therefore, the LPP may serve as a biomarker of cue reactivity change observed after TMS treatment. Specifically, measuring both RewP and LPP will provide critical information on whether TMS alters overall reward functioning or a bias toward drug rewards compared to non-drug rewards. It is unknown if stimulation to the dIPFC or dmPFC would be more effective in manipulating the LPP amplitude. fMRI studies of cue reactivity implicate dIPFC and dmPFC in the processing of drug cues in addiction⁹⁰, so both stimulation sites should have an effect on LPP to drug/non-drug cues.

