Concomitant Medications Tracking Log	X	X	X	X
Columbia Suicidal Severity Rating Scale (C-SSRS)	X	X	X	X
Danger Assessment Tool	X	X	X	X
Cocaine Selective Severity Assessment (CSSA)		X	X	X
Hours of Sleep		X	X	X
TMS Side Effects Questionnaire*		X	X	X
Pain Visual Analogue Scale (VAS)*		X	X	X
Montreal Cognitive Assessment (MoCA)*		X	X	X
TMS				
Intermittent theta burst stimulation 3x with 15-minute intervals in between		X	X	X
Study Manipulation Measures				
Blinding Question		X	X	X
Main Outcomes				
EEG (Doors Task & Picture Viewing		X	X	X

Task)*				
Behavioral Reward (Pavlovian Go/No-Go)*		X	X	X
Other Measures/Outcomes				
Minnesota Cocaine Craving Scale (MCCS)*	X	X	X	X
Snaith-Hamilton Anhedonia Scale (SHAPS)*	X	X	X	X
Cocaine Use Timeline Follow Back (TLFB)	X	X	X	X
Barratt Impulsiveness Scale (BIS-11)	X			
PROMIS Sleep Disturbance/Impairment		X	X	X
Profile of Mood States (POMS)		X	X	X
Delay Task*		X	X	X
Cocaine Purchasing Task	X			

¹dorsolateral prefrontal cortex; ²dorsomedial prefrontal cortex; * measured before and after TMS

EEG Measures. During the tasks described below, EEG will be collected using a 64-channel actiCAP electrode cap, amplified with BrainAmp MR and digitized using Brain Vision Recorder (Brain Products, Munich). Impedances will be maintained below 50 k(OHM). The sampling rate will be 500 Hz and data will be filtered with .1 Hz high-pass and 100 Hz low-pass filters. Data reduction will be performed with Brain Vision Analyzer 2, MATLAB, and BESA. Both ERP (mean amplitude) and TFA approaches will be used to analyze the RewP. While the main hypotheses will look at delta power, we will also examine changes in other frequencies, including theta, in exploratory analyses. The LPP will be defined as the mean amplitude between 400-800ms post stimulus^{47,81} and a difference score (cocaine minus pleasant) will be used to assess LPP bias.

Reward Sensitivity. The Doors Task⁵⁹ will be used to elicit the RewP. Participants guess which door contains a reward behind it. After selecting a door, the participants are notified if they won by a green arrow pointing up or if they lost by a red arrow pointing down. Unknown to the participants, winning and losing outcomes are presented 50% of the time in a random order. Self-reported anhedonia (Snaith Hamilton Pleasure Scale; SHAPS) will also be assessed at each visit as a secondary measure of reward sensitivity.

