Cue Reactivity. The Picture Viewing Task will be used to elicit the LPP, reflecting the motivational salience of a stimulus. During this task, participants are asked to view a slideshow of images including pleasant, unpleasant, neutral, and cocaine-related images⁶¹.

Cocaine Craving. Cocaine craving will be measured using the Minnesota Cocaine Craving Scale (MCCS)¹⁰³. The MCCS is a widely used and reliable self-report measure of craving for cocaine. It will be assessed before and after each iTBS session.

Behavioral Reward Learning. Participants will complete a Pavlovian Go/No-Go task to assess Pavlovian influences on instrumental learning¹⁰⁷⁻¹¹⁰. In the first “learning” phase, participants learn whether to press a button or withhold a response to receive a monetary reward or avoid a loss. In the second “transfer” phase, participants perform a forced choice task, where each of the predictive cues in the learning phase are paired with each other. Participants must select the “most rewarding” cue.

Delay Discounting and Cocaine Demand. Both delay discounting and cocaine demand are measures that provide information about cost-benefit trade-offs and are often associated with substance use outcomes. Previous studies have shown that TMS might alter these principles¹¹¹. The delay task will specifically measure delay discounting and will consist of 5 questions about whether the participant would hypothetically like to receive less money now or more money later¹¹². The cocaine purchasing task will be used to assess how much cocaine the participant would be willing to use given incremental cost of cocaine^{113,114}.

Safety/Other outcomes. We will collect the following day-of measures before iTBS sessions: Profile of Mood States (POMS)¹¹⁵, hours of sleep, Patient-Reported Outcomes Measurement Information System (PROMIS) Sleep Disturbance (SD) and Sleep-Related Impairment (SRI) short forms^{116,117}, UDS/TLFB, breathalyzer, withdrawal (Cocaine Selective Severity Assessment; CSSA¹¹⁸), and the TMS AE/SAE form. The TMS AE/SAE form will also be completed after iTBS sessions. The Montreal Cognitive Assessment (MoCA)¹⁰⁴ will be used to assess for changes in cognition and will be administered before and after the 3 iTBS sessions.

Analysis Plan

Pilot Study

Data Analytic Strategy.

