Modeling Assumptions. Evaluation of assumptions for frequentist models will use graphical evidence (e.g., residual plots) and formal statistical tests. Bayesian convergence and modeling assumptions will be evaluated by effective sample size, scale reduction factors ("rhat"), and posterior predictive checking. Violated assumptions will be addressed via model re-specification, variable transformation, robust estimation, stratification, and/or coefficient scaling where appropriate. **Intention-to-treat (ITT)** primary analyses will include all randomized participants; follow-up analyses may evaluate modified ITT samples should specific participants merit exclusion (e.g., randomized but never initiated the trial). A per protocol analysis will complement the primary ITT analysis as due diligence. **Missing data** patterns will be evaluated using Little's Test of Missing Completely at Random (MCAR)¹³⁶ for continuous outcomes and the Park and Lee approach¹³⁷ for discrete outcomes. Models will handle missingness via maximum likelihood, explicit modeling of missingness¹³⁸, and/or imputation with sensitivity analyses to evaluate the robustness of findings. Each approach is

robust to ignorable missingness (i.e., missing completely at random and missing at random). Pattern-mixture modeling will be used to address identified non-ignorable missing data patterns¹³⁹.

Specific Analyses

All statistical models (described below) will account for correlated observations via the best-fitting structure of random effects (i.e., lowest information criteria) found when fitting level-2 intercepts and/or slopes) for repeated measures (where necessary) and statistically control for potential confounders as defined above. Outcome variables will be modeled as difference scores to account for the pre/post design (i.e., post-iTBS minus pre-iTBS).

Hypothesis 1a (Primary): Active iTBS relative to sham will increase the amplitude of the RewP/delta power to rewards compared to non-rewards. GLMM will model the change in amplitude of the RewP/delta power to rewards as a function of iTBS condition, with random effects to account for repeated measures.

Hypothesis 1b (Exploratory): iTBS to dmPFC will result in a greater increase in the RewP/delta power compared to dPFC. Follow-up testing of the model described above for Hypothesis 1a will evaluate pairwise comparisons between iTBS conditions.

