Hypothesis 2a (Primary): Active iTBS relative to sham will switch the drug>pleasant LPP bias. GLMM will model the change in LPP bias as a function of iTBS condition.

Hypothesis 2b (Exploratory): iTBS to dmPFC will result in a greater increase in LPP bias (i.e., greater LPP to pleasant images compared to cocaine images). Follow-up testing of the model for Hypothesis 2a will evaluate pairwise comparisons between iTBS conditions.

Hypothesis 3a (Exploratory): Analyses will explore baseline CUD severity, impulsivity, and craving as predictors of iTBS effects on EEG. GLMM will model EEG outcomes as a function of the interaction between iTBS condition and each named predictor (in separate models): baseline CUD severity, impulsivity, and craving, controlling for constituent main effects.

Sample Size and Power Analysis

The current proposal is powered with respect to the primary hypothesis in the study (Hypothesis 1a). G*Power v. 3.1.9.4 provides calculations from the frequentist perspective via a within-factor repeated measures model, a simplified version of the GLMM described above. Assuming a correlation among repeated measures $r = 0.50$ and two-tailed $\alpha = 0.05$, the current feasible sample size $N = 75$ provides 80% power to detect an effect size as small as Cohen's $f = 0.149$ (comparable to a small-to-moderate Cohen's $d = 0.30$). These estimates also broadly apply to Hypothesis 2a. Bayesian analyses proposed above will then provide a complementary analysis of all models that yields probabilistic estimates for all model effects, even in the context of relatively smaller sample sizes¹⁴⁰ (i.e., the available data for subgroup analyses or higher-complexity models).

Protection of Human Subjects

Inclusion Criteria:

1. be between 18 and 65 years of age at the time of the first study visit (iTBS session day)
2. meet DSM-5 criteria for current cocaine use disorder of at least moderate severity (≥ 4 symptoms)
3. have at least 1 positive urine BE specimen (≥ 300 ng/mL) during intake
4. be able to understand the consent form and provide written informed consent
5. be able to provide the following verifiable information for a minimum of 2 contact persons: full legal name, email address, local mailing address, and as applicable, home, work, and cell phone numbers

Exclusion criteria:

1. current DSM-5 diagnosis for substance use disorder (of at least moderate severity) other than cocaine, marijuana, or nicotine

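### Main trial: exploratory Hypothesis 2b, as worded in the Aims, is not tested by the cocaine-minus-pleasant LPP score that the analysis plan assigns to it

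*Combined protocol and SAP*

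**What the plan says.** All of this concerns the main trial.

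- **Hypothesis in the Aims.** Under Aim 2, Hypothesis 2b reads: "iTBS to dmPFC will result in a greater increase in LPP to pleasant images". No other image type is mentioned.
- **Hypothesis in Specific Analyses.** The same label now reads: "iTBS to dmPFC will result in a greater increase in LPP bias (i.e., greater LPP to pleasant images compared to cocaine images". This is a relative quantity.
- **Score.** EEG Measures defines the LPP as a mean amplitude over 400-800 ms and adds that "a difference score (cocaine minus pleasant) will be used to assess LPP bias". Specific Analyses models outcomes as post minus pre.
- **Model.** For Hypothesis 2a, "GLMM will model the change in LPP bias as a function of iTBS condition". Hypothesis 2b is a follow-up to that model, by pairwise contrasts of conditions. Image type is not a factor.
- **Data.** Cue Reactivity says participants view "a slideshow of images including pleasant, unpleasant, neutral, and cocaine-related images". EEG is recorded before and after stimulation at each visit. No main-trial analysis is specified for the neutral or unpleasant images.
- **Pilot, for contrast.** The pilot's LPP model has image type as a factor with all four levels.

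**The concern.** One label covers two different quantities. The Aims speak of the absolute response to pleasant images. The analysis looks at the gap between two responses, and that gap can close from either side.

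Two things are at stake. A dmPFC contrast on the bias score could be reported as support for the Aims' hypothesis when the pleasant-image response was flat or had fallen. A true rise in that response could also be missed if the cocaine response rose with it. Separately, a positive Hypothesis 2a result would not show whether stimulation lowered the cocaine response, raised the pleasant one, or blunted both unequally.

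**Working it through.** **The plan's own figure.** Sample Size and Power Analysis gives 80% power at N = 75, f = 0.149, r = 0.50 and two-tailed alpha 0.05, and says this broadly applies to Hypothesis 2a. With m = 3 conditions and sphericity assumed, lambda = f² × N × m / (1 - r) = 0.0222 × 75 × 3 / 0.5 = 9.99, on 2 and 148 degrees of freedom. Power is 80.7%, so the figure reproduces. It does not decide this point, which concerns what the score measures.

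**Algebra.** Let C and P be the differences between dmPFC and a comparator condition in the post-minus-pre change in cocaine-image and pleasant-image LPP.

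- Quantity in the Aims' Hypothesis 2b: P.
- Quantity tested: B = C - P.

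B determines P only if C is known. The plan neither fixes nor estimates C. Hypothetical values in microvolts:

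| C | P | B = C - P | Pleasant response |
|---|---|---|---|
| -2 | 0 | -2 | unchanged |
| 0 | +2 | -2 | rises |
| -3 | -1 | -2 | falls |
| +2 | +2 | 0 | rises |

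The first three rows cannot be told apart on B. The fourth shows no change in B although the Aims' hypothesis is true. The planned Bayesian models inherit the same limit where they use the same outcome.

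**Illustration.** The documents give no SD or expected effect for the LPP, so these are assumptions: each image-type change score has SD 1, all pairwise correlations are 0.5, N = 75, two-sided alpha 0.05. A paired active-versus-sham t test on change scores was simulated 4,000 times per case. As a check, B combines four scores, so its variance is 4 × (1 - 0.5) = 2 and its standard error √(2/75) = 0.163. P combines two, so its variance is 1 and its standard error √(1/75) = 0.115. An effect of 0.4 is then 2.45 standard errors on B and 3.46 on P.

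| Case (C, P), neutral unchanged | Bias score | Pleasant alone | Pleasant minus neutral |
|---|---|---|---|
| (0, +0.4) | 68% | 94% | 68% |
| (-0.4, 0) | 68% | 5% | 5% |
| (-0.6, -0.2) | 69% | 39%, a fall | 22%, a fall |
| (+0.4, +0.4) | 5% | 94% | 68% |

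Entries are rejection rates. The bias score rejects equally often whether the pleasant response rises, stays flat or falls. The pleasant-image change separates these cases.

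**The case against.** The strongest reply is that the primary endpoint matches its question. Hypothesis 2a is about the gap between drug and pleasant responses, and the primary outcome is defined on that comparison. Equal blunting of both responses is then correctly a null result. This stands, and the score should stay for Hypothesis 2a.

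It can also be said that Specific Analyses makes Hypothesis 2b relative, so that (-3, -1) does support it, and that rewording the Aims would remove the mismatch. That is one way to reconcile the two statements. It would still leave the pleasant and cocaine responses unreported and the source of a Hypothesis 2a effect unknown.

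A reader might infer that Hypothesis 2b is untestable. The documents do not support that. The pleasant-image LPP is recorded before and after stimulation, EEG Measures reserves the difference score for bias only, and Probability and Inference provides for exploratory and post hoc analyses under FDR. The hypothesis is not tested by the specified analysis, which is a narrower statement.

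A reader might also infer that the trial cannot settle "whether TMS alters overall reward functioning or a bias toward drug rewards compared to non-drug rewards". The protocol assigns that question to the RewP and the LPP together, so it does not depend on splitting the LPP.

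Finally, replacing the score with pleasant minus neutral would repeat the problem, since that too is a difference score and the Aims name no neutral reference. This is right. The direct test is the pleasant-image change, with neutral-referenced contrasts as support.

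**Conclusion.** The point holds for the main trial, as a moderate one. The specified analysis does not test Hypothesis 2b as the Aims word it, and it leaves the source of any Hypothesis 2a effect ambiguous. This follows from the definition of the score and needs no assumption about effect size. The microvolt values are hypothetical, and the rejection rates depend on the assumed SD and correlation.

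Hypothesis 2b is exploratory. The primary endpoint for Hypothesis 2a, its error rate and the stated power are unaffected. So is the pilot, which the protocol says is registered as a separate record from the main trial. Hypothesis 3a speaks only of EEG outcomes in general and concerns moderators, so it does not fill the gap.

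**What to change.** 1. Reconcile the two statements of Hypothesis 2b and name the comparator, which neither gives. Settle the sign as well: with bias scored as cocaine minus pleasant, an increase means relatively more response to cocaine, the opposite of the gloss in Specific Analyses.
2. Keep the bias score for Hypothesis 2a.
3. Pre-specify, in the exploratory FDR set, the change in pleasant-image LPP by condition (dmPFC versus dlPFC, and dmPFC versus sham) as the test of Hypothesis 2b as worded in the Aims.
4. Report the changes in cocaine-image and neutral-image LPP beside it, with pleasant minus neutral and cocaine minus neutral as supporting contrasts. The neutral-image change shows whether a shift is common to all images, which the neutral-referenced contrasts alone would cancel.
5. Claim an increased response to pleasant images only if the pleasant-image LPP itself rises.

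The cost is wording and a few extra exploratory contrasts, with a slightly larger FDR set. No new recordings, visits or participants are needed. Fixing the contrasts now also prevents choosing a component after seeing the results.
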